12.2.1 Hypoglycemia Event

Hypoglycemia not associated with an Adverse Device Effect is only reportable as an adverse event when the following definition for severe hypoglycemia is met:

- The event required assistance of another person due to altered consciousness, and required another person to actively administer carbohydrate, glucagon, or other resuscitative actions.
- Impaired cognitively to the point that he/she was unable to treat himself/herself, was unable to verbalize his/ her needs, was incoherent, disoriented, and/or combative, or experienced seizure or coma. These episodes may be associated with sufficient neuroglycopenia to induce seizure or coma.
- If plasma glucose measurements are not available during such an event, neurological recovery attributable to the restoration of plasma glucose to normal is considered sufficient evidence that the event was induced by a low plasma glucose concentration.

12.2.2 Hyperglycemia Events/Diabetes Ketoacidosis

Hyperglycemia not associated with an Adverse Device Effect is only reportable as an adverse event when one of the following four criteria is met:

MiniNET 25-Oct-2024 Page 44 of 60

940

941

942

943

944

945

947

948

949

950

955

961

962

963 964

965

966

967 968

969

970

971

- The event involved DKA, as defined by the Diabetes Control and Complications Trial (DCCT) and described below.
 - Evaluation or treatment was obtained at a health care provider facility for an acute event involving hyperglycemia or ketosis.
 - Blood ketone level ≥ 1.5 mmol/L and communication occurred with a health care provider at the time of the event.
 - Blood ketone level \geq 3.0 mmol/L, even if there was no communication with a health care provider.
- 946 Hyperglycemic events are classified as DKA if the following are present:
 - Symptoms such as polyuria, polydipsia, nausea, or vomiting.
 - Serum ketones ≥1.5 mmol/L or large/moderate urine ketones.
 - Either arterial blood pH <7.30 or venous pH <7.24 or serum bicarbonate <15.
 - Treatment provided in a health care facility.
- 951 All reportable Adverse Events—whether volunteered by the participant, discovered by study
- 952 personnel during questioning, or detected through physical examination, laboratory test, or other
- 953 means—will be reported on an adverse event form online. Each adverse event form is reviewed
- by the Medical Monitor to verify the coding and the reporting that is required.

12.3 Relationship of Adverse Event to Study Device

- The study investigator will review each adverse event and assess the relationship of any adverse
- event to be related or unrelated by determining if there is a reasonable possibility that the adverse
- event may have been caused by the study device.
- To ensure consistency of adverse event causality assessments, investigators should apply the following general guideline when determining whether an adverse event is related:
 - RELATED: There is a plausible temporal relationship between the onset of the adverse event and the study intervention, and the adverse event cannot be readily explained by the participant's clinical state, intercurrent illness, or concomitant therapies; and/or the adverse event follows a known pattern of response to the study intervention; and/or the adverse event abates or resolves upon discontinuation of the study intervention or dose reduction and, if applicable, reappears upon re-challenge.
 - UNRELATED: Evidence exists that the adverse event has an etiology other than the study intervention (e.g., preexisting medical condition, underlying disease, intercurrent illness, or concomitant medication); and/or the adverse event has no plausible temporal relationship to study intervention.

12.4 Intensity of Adverse Event

The intensity of an adverse event will be rated on a three-point scale: (1) mild, (2) moderate, or (3) severe. It is emphasized that the term severe is a measure of intensity: thus, a severe adverse event

MiniNET 25-Oct-2024 Page 45 of 60

- 974 is not necessarily serious. For example, itching for several days may be rated as severe, but may 975 not be clinically serious.
 - MILD: Usually transient, requires no special treatment, and does not interfere with the participant's daily activities.
 - MODERATE: Usually causes a low level of inconvenience or concern to the participant and may interfere with daily activities but is usually ameliorated by simple therapeutic measures.
 - SEVERE: Interrupts a participant's usual daily activities and generally requires systemic drug therapy or other treatment.

12.5 Coding of Adverse Events

- Adverse events will be coded per standard categories (i.e., mild, moderate, severe). The Medical
- Monitor will review the investigator's assessment of causality and may agree or disagree. Both
- 986 the investigators and Medical Monitor's assessments will be recorded. The Medical Monitor will
- have the final say in determining the causality.
- Adverse events that continue after the participant's discontinuation or completion of the study will
- be followed until their medical outcome is determined or until no further change in the condition
- 990 is expected.

976

977

978

979

980

981

982

983

991

993

994

995

996

997 998

999

1000

1001

1002

1003

1004 1005

1006

1007

1008

1009

1010

12.6 Outcome of Adverse Events

- The outcome of each reportable adverse event will be classified by the investigator as follows:
 - RECOVERED/RESOLVED The participant recovered from the AE/SAE without sequelae. Record the AE/SAE stop date.
 - RECOVERED/RESOLVED WITH SEQUELAE The event persisted and stabilized without change in the event anticipated. Record the AE/SAE stop date.
 - FATAL A fatal outcome is defined as the SAE that resulted in death. Only the event that was the cause of death should be reported as fatal. AEs/SAEs that were ongoing at the time of death; however, were not the cause of death, will be recorded as "resolved" at the time of death.
 - NOT RECOVERED/NOT RESOLVED (ONGOING) An ongoing AE/SAE is defined as the event was ongoing with an undetermined outcome.
 - An ongoing outcome will require follow-up by the site in order to determine the final outcome of the AE/SAE.
 - The outcome of an ongoing event at the time of death that was not the cause of death, will be updated and recorded as "resolved" with the date of death recorded as the stop date.
 - UNKNOWN An unknown outcome is defined as an inability to access the participant or the participant's records to determine the outcome (for example, a participant that was lost to follow-up).

MiniNET 25-Oct-2024 Page 46 of 60

- 1011 All clinically significant abnormalities of clinical laboratory measurements or adverse events
- 1012 occurring during the study and continuing at study termination should be followed by the
- participant's physician and evaluated with additional tests (if necessary) until diagnosis of the
- underlying cause, or resolution. Follow-up information should be recorded on source documents.
- 1015 If any reported adverse events are present when a participant completes the study, or if a participant
- 1016 is withdrawn from the study due to an adverse event, the participant will be contacted for re-
- evaluation within 2 weeks. If the adverse event has not been resolved, additional follow-up will be
- performed as appropriate. Every effort should be made by the Investigator or delegate to contact
- the participant until the adverse event has resolved or stabilized.

1020 **12.7 Reportable Device Issues**

- All UADEs, ADEs, device complaints, and device malfunctions will be reported irrespective of
- whether an adverse event occurred, except in the following circumstances.
- The following device issues are anticipated and will not be reported but will report as an Adverse
- 1024 Event if the criteria for AE reporting described above are met:
- Component disconnections

1026

1028

1029

1030

1031

1032

1033 1034

1035

1036

1037

1038

1039

1040 1041

1042

1043

1044 1045

1046 1047

1048

- CGM sensors lasting fewer than the number of days expected per CGM labeling
- CGM tape adherence issues
 - Pump infusion set occlusion not leading to ketosis
 - Battery lifespan deficiency due to inadequate charging or extensive wireless communication
 - Intermittent device component disconnections/communication failures not leading to system replacement
 - Device issues clearly addressed in the user guide manual that do not require additional troubleshooting
 - Skin reactions from CGM sensor placement or pump infusion set placement that do not meet criteria for AE reporting

12.8 Timing of Event Reporting

- UADEs must be reported within 10 working days to the FDA after the sponsor first receives notice of the adverse effect.
- Other reportable adverse events, device malfunctions (with or without an adverse event) and device complaints should be reported promptly, but there is no formal required reporting period.
- The IDE Sponsor will investigate the UADE and if indicated, report the results of the investigation to the IRBs, FDA, and Medical Monitor within 10 working days of the study team becoming aware of the UADE per 21CFR 812.46(b) (2).
- The Medical Monitor will determine if the UADE presents an unreasonable risk to participants. If so, the Medical Monitor must ensure that all investigations, or parts of investigations presenting that risk, are terminated as soon as possible but no later than

MiniNET 25-Oct-2024 Page 47 of 60

- 5 working days after the Medical Monitor makes this determination and no later than 1050 15 working days after first receipt notice of the UADE.
 - In the case of a device system component malfunction (e.g. pump, CGM, control algorithm), information will be forwarded to the responsible manufacturer by the study personnel.

12.9 Stopping Criteria

1051 1052

1053

1054

1055

1056

1057

1058 1059

1060

1061 1062

1063 1064

1065

1080

12.9.1 Participant Discontinuation

A participant will be discontinued if any of the following occur:

- The investigator believes it is unsafe for the participant to continue the intervention. This could be due to the development of a new medical condition or worsening of an existing condition; or participant behavior contrary to the indications for use of the device that imposes on the participant's safety
- The participant requests that the treatment be stopped
- Two distinct episodes of DKA
- Two distinct severe hypoglycemia events as defined in section 12.2.1.
- Two events of any kind: severe hypoglycemia or DKA

12.9.2 Suspending/Stopping Overall Study

- In the case of an unanticipated system malfunction resulting in a severe hypoglycemia or severe hyperglycemia event (as defined in section 12.2.2), use of the study device system will be suspended while the problem is diagnosed.
- In the event that two distinct episodes of DKA or two distinct severe hypoglycemia events as defined in section 12.2.1 occur, the overall study would be suspended while the underlying conditions are determined.
- 1072 In addition, study activities could be similarly suspended if the manufacturer of any constituent
- study device requires stoppage of device use for safety reasons (e.g., product recall). The affected
- study activities may resume if the underlying problem can be corrected by a protocol or system
- modification that will not invalidate the results obtained prior to suspension. The study Medical
- Monitor will review all adverse events and adverse device events that are reported during the study
- and will review compiled safety data at periodic intervals. The Medical Monitor may request
- suspension of study activities or stoppage of the study if deemed necessary based on the totality
- of safety data available.

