7.6.1 Hypoglycemia

- a. If CGM falls below 70 mg/dL at any time, confirm <70mg/dL CGM readings and potential hypoglycemia symptoms with a fingerstick blood glucose. If blood glucose confirms <70mg/dL CGM reading, hypoglycemia will be treated with oral glucose of approximately 5-15 g. Participants will be encouraged to wait 15 min prior to giving a second glucose treatment. These fingerstick checks will be performed during the hotel stay and during the home portion if the participant chooses to do so. During the hotel stay we will also recheck a fingerstick blood glucose before retreatment.
- b. If a participant experiences any symptoms of hypoglycemia (e.g., shakiness, dizziness, sweating, pallor, clumsiness, difficulty paying attention, or tingling around the mouth), then the participant should treat with oral glucose of 5-15 g. Participants will be encouraged to wait 15 min prior to giving a second glucose treatment. During the hotel portion of the study, a fingerstick blood glucose will be assessed before such treatment for symptoms and before any re-treatment.
- c. If a participant displays any signs of neuroglycopenia (e.g., lethargy, disorientation, confusion, or inappropriate behavior) or severe hypoglycemia (e.g., hypoglycemic seizure, loss of consciousness, inability to properly consume treatment) hypoglycemia will be treated with either oral glucose or glucagon. The patient will be discharged from the study. The participant should consult with a study physician to discuss next steps for broader evaluation of symptoms unrelated to hypoglycemia.

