11.1.11 Risk Assessment

- Based on the facts that (1) adults and adolescents with diabetes experience mild hypoglycemia and
- 850 hyperglycemia frequently as a consequence of the disease and its management, (2) the study
- intervention involves periodic automated insulin dosing that may increase the likelihood of
- 852 hypoglycemia, and periodic automated attenuation of insulin delivery that may increase the
- likelihood of hyperglycemia, (3) mitigations are in place, and have been tested in prior studies
- using the investigational device system in the home setting, that limit the likelihood of excessive
- insulin dosing or prolonged withdrawal of insulin, and (4) rapid reversal of hypoglycemia and
- 856 hyperglycemia can be achieved, it is the assessment of the investigators that this protocol falls
- under DHHS 46.405 which is a minor increase over minimal risk. In addition, it is the belief of the
- 858 investigators that this study also presents prospects of direct benefit to the participants and general
- benefit to others with diabetes.

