12.10 Independent Safety Oversight

- 1081 A Medical Monitor will review all DKA and severe hypoglycemia irrespective of relatedness to
- study device use, and all serious events (including UADEs) related to study device use at the time
- of occurrence. The Medical Monitor can request modifications to the study protocol or suspension
- or outright stoppage of the study if deemed necessary based on the totality of safety data available.

MiniNET 25-Oct-2024 Page 48 of 60

Details regarding the Medical Monitor review will be documented in a separate Medical Monitor document.

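### Section 12.9.2 pauses the study after two DKA or two severe hypoglycemia events, but not after one of each

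*Combined protocol and SAP*

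**What the plan says.** Section 12.9.2 has two event-based triggers.

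- **Malfunction trigger.** It begins "In the case of an unanticipated system malfunction resulting in a severe hypoglycemia or severe hyperglycemia event (as defined in section 12.2.2") and suspends use of the device system after a single such event.
- **Count trigger.** It suspends the overall study "In the event that two distinct episodes of DKA or two distinct severe hypoglycemia events" (the latter by the Section 12.2.1 definition) have occurred. It is not limited to time on AIDANET, and it does not say whether the two events may come from different participants.

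Section 12.9.1 discontinues a participant after two DKA episodes, after two severe hypoglycemia events, and also after "Two events of any kind: severe hypoglycemia or DKA".

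Three other places bear on the point.

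- **Section 7.6.1, item c.** After signs of neuroglycopenia or severe hypoglycemia on AIDANET: "The patient will be discharged from the study".
- **Section 12.10.** "A Medical Monitor will review all DKA and severe hypoglycemia irrespective of relatedness to" device use, at the time of occurrence. The Monitor can request suspension or stoppage. Chapter 9 says the same, and Section 12.9.2 repeats the power to request it.
- **Sections 12.2.1 and 12.2.2.** Section 12.2.1 makes hypoglycemia reportable "when the following definition for severe hypoglycemia is met". Section 12.2.2 opens "Hyperglycemia not associated with an Adverse Device Effect is only reportable as an adverse event when one of the following four criteria is met", lists the four criteria and then defines DKA. It does not use the term severe hyperglycemia.

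**The concern.** The plan pools the two event types for one person but not across the study, and gives no reason for the difference. The two types can share a cause. Section 11.1.11 says that the intervention involves automated dosing that can raise the chance of "hypoglycemia, and periodic automated attenuation of insulin delivery that may increase the" likelihood of hyperglycemia. One severe low and one DKA on the new code could therefore both be signals about the same algorithm.

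Section 14.1 allows up to 6 participants per session, so the whole planned cohort could be on the device when the second event happens. For a mixed pair, whether the others pause then rests on judgement and not on the stated rule.

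**Working it through.** **1. Which event counts escape the rule.** The current rule is SH ≥ 2 or DKA ≥ 2, where SH is severe hypoglycemia. A pooled rule is SH + DKA ≥ 2. Enumerating counts of 0 to 3 for each type, the rules differ in one case only: SH = 1 and DKA = 1.

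**2. Where that case is left open.** If an unanticipated malfunction caused the severe hypoglycemia, the first trigger already suspends device use. A malfunction-caused DKA would do so too on any sensible reading of Section 12.2.2. A severe low on AIDANET takes that participant out (Section 7.6.1), so the pair would arise mostly across participants, where only Section 12.9.2 applies.

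**3. How often.** The documents give no event rates and no operating characteristics for the rule, so there is no stated figure to reproduce. The inputs are:

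- Exposed n = 6. This is the planned number of completers. The 12 in Section 3.2 is an enrollment cap that allows for dropouts and screen failures, and Chapter 5 replaces participants only before hotel admission.
- Per-participant risks s (SH) and d (DKA). These are assumed, independent, with at most one event of each type per participant.
- About 9 days of AIDANET use (Section 8.1 ends use on overall study day 9), used only to turn risks into rates.

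P(exactly one of each) = [6s(1−s)^5] × [6d(1−d)^5].

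At s = d = 0.01: 6 × 0.01 × 0.99^5 = 0.05706, and 0.05706² = 0.003256, about 0.3%.

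P(current rule) = 1 − [1 − P(SH ≥ 2)] × [1 − P(DKA ≥ 2)]. The pooled rule adds the mixed pair to this. Given one of each, the chance that both fall in the same participant is 1/6, so 5/6 of pairs are in different participants. Rate per person-year = −ln(1−p)/(9/365.25).

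| Assumed risk, each | One of each | In different participants | Current rule | Pooled rule | Rate per person-year, each |
|---|---|---|---|---|---|
| 0.1% | 0.004% | 0.003% | 0.003% | 0.007% | 0.04 |
| 0.5% | 0.09% | 0.07% | 0.07% | 0.16% | 0.2 |
| 1% | 0.33% | 0.27% | 0.29% | 0.62% | 0.4 |
| 2% | 1.2% | 0.98% | 1.1% | 2.3% | 0.8 |
| 5% | 5.4% | 4.5% | 6.5% | 11.8% | 2.1 |

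With unequal risks, the mixed pair has probability 0.03% (SH 1%, DKA 0.1%) or 1.3% (SH 5%, DKA 1%).

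Within this model the figures overstate the uncovered case, because pairs that include a malfunction-caused event already suspend device use. They are not bounds outside it: a shared fault would make the two event types dependent. The 5% row is a stress case, since Section 3.5 excludes people with DKA, or with severe hypoglycemia involving seizure or loss of consciousness, in the past 12 months.

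**The case against.** The strongest reply is that the gap has a live safeguard. The Medical Monitor sees every DKA and every severe hypoglycemia as it occurs, whether or not it is thought related, and can ask for suspension or stoppage. For a rare pair in a 6-person study, real-time judgement in place of an automatic count is a defensible design preference. The separate Medical Monitor document may already deal with it. All of this stands and keeps the point small. What it does not do is explain why two events of one type call for an automatic pause while one of each does not, when the participant-level rule treats them alike.

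Three stronger readings are tempting, and the documents do not support them.

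- **A mixed pair would go unchecked.** It would not, given the Monitor's review in Chapter 9 and Sections 12.9.2 and 12.10.
- **The mandatory termination route in Section 12.8 is closed, because Sections 11.1.4 and 11.1.5 already name hypoglycemia, seizures and ketonemia.** The UADE definition in Section 12.1.3 also covers effects not previously identified in severity or degree of incidence. Section 11.1.5 does not name DKA, and Section 11.1.4 expects hypoglycemia to be no more frequent than in daily life. A device-associated pair could qualify. The route still needs that association and a finding of unreasonable risk.
- **The malfunction trigger cannot work because severe hyperglycemia is undefined.** Section 12.2.2 does hold criteria, and staff would sensibly apply them. What is open is whether DKA alone or any of the four criteria is meant, which is a loose cross-reference.

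**Conclusion.** The inconsistency between Sections 12.9.1 and 12.9.2 stands and is worth correcting at low priority. It concerns one event pattern, mainly across participants on AIDANET and without a malfunction, and discretionary oversight covers much of it. Its probability is about 0.3% at an assumed 1% risk of each event, and runs from 0.004% to 5.4% over assumed risks of 0.1% to 5%. All of these rest on independence and 6 exposed, not on any rate in the protocol. If the separate Medical Monitor document already requires a pause after a mixed pair, the point is met there.

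The malfunction trigger's reference to Section 12.2.2 is a wording query only.

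**What to change.** Replace the count trigger in Section 12.9.2 with one rule that matches Section 12.9.1 and has one scope for all pairs:

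> If any two distinct events, each being severe hypoglycemia (Section 12.2.1) or DKA (Section 12.2.2), occur in the same or different participants, the overall study will be suspended until their underlying causes have been determined.

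The mixed pair should not be limited to AIDANET use while same-type pairs stay unrestricted. Two severe lows in usual care would then pause the study, but one low and one DKA in usual care would not.

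The cost is one sentence and a rare extra temporary pause, with the probability given above for one of each. Events in the usual-care week would count, as they do now; the risk to enter in the formula is then the one over the longer period. Endpoints, sample size and analysis do not change.

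Separately, ask the sponsor which Section 12.2.2 criterion the malfunction trigger means, and add a Section 12.2.1 reference there for severe hypoglycemia. That reference is useful because the exercise metrics in Section 14.3.2 gloss SH as CGM below 70 mg/dL for more than 15 minutes, which is much milder than Section 12.2.1.

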12.10 Independent Safety Oversight

- 1081 A Medical Monitor will review all DKA and severe hypoglycemia irrespective of relatedness to
- study device use, and all serious events (including UADEs) related to study device use at the time
- of occurrence. The Medical Monitor can request modifications to the study protocol or suspension
- or outright stoppage of the study if deemed necessary based on the totality of safety data available.

MiniNET 25-Oct-2024 Page 48 of 60

Details regarding the Medical Monitor review will be documented in a separate Medical Monitor document.
